1.1. Schedule of Activities

Table 1: Schedule of Activities for Study MVT-601-3003

PERIOD	OPEN-LABEL TREATMENT									SAFETY FOLLOW-UP
	VISIT NAME (Timing is relative to MVT-601-3001/-3002)	Week 24/Baseline (Week 24 of Parent Study; Baseline of Extension Study)	Week 28	Week 32	Week 36	Week 40	Week 44	Week 48	Week 52 ^a (or Early Termination of Study Drug)	
Visit Window (days)	Parent Study Day 169 - 10 to + 20	± 7	± 7	± 7	± 7	± 7	± 7	± 10	-	- 3 to + 18
Informed Consent	X ^d									
Review Eligibility Criteria	X									
Concomitant Medications ^e	X ^f	X	X	X	X	X	X	X	X	X
Vital Signs (BP, HR, Temperature)	X ^g	X	X	X	X	X	X	X	X ^h	X
Weight	X ^g			X				X	X ^h	
Complete Physical Examination	X ^g							X		
Visual Acuity ⁱ	X ^g									
Signs and Symptoms-Directed Physical Examination ⁱ		X	X	X	X	X	X		X ^h	X
12-Lead ECG ^k	X ^g							X	X ^h	
Clinical Laboratory Tests ^l	X ^{g,m}	X	X	X	X	X	X	X ^m	X ^h	X
Pharmacodynamics Sample ⁿ	X ^{g,m}							X ^m	X ^{h,m}	
Urinalysis	X ^g							X	X ^h	
Pregnancy Test (Urine)	X ^g	X	X	X	X	X	X	X	X ^h	X

PERIOD	OPEN-LABEL TREATMENT									SAFETY FOLLOW-UP
VISIT NAME (Timing is relative to MVT-601-3001/-3002)	Week 24/Baseline (Week 24 of Parent Study; Baseline of Extension Study)	Week 28	Week 32	Week 36	Week 40	Week 44	Week 48	Week 52 ^a (or Early Termination of Study Drug)	Un-scheduled ^b	Follow-Up ^c (~30 days after last dose of study drug)
Visit Window (days)	Parent Study Day 169 - 10 to + 20	± 7	± 7	± 7	± 7	± 7	± 7	± 10	-	- 3 to + 18
Transvaginal Ultrasound ^o	X ^g							X ^p	X ^h	
Bone Densitometry ^d	X ^g			X				X ^{p,r}	X ^h	
Endometrial Biopsy	X ^{g,s}							X ^p	X ^h	
Dispense Study Treatment	X	X	X	X	X	X	X		X ^h	
Patient Paper Diary ^t	X	X	X	X	X	X	X	X	X	
Dispense Feminine Products	X	X	X	X	X	X	X		X ^h	
Feminine Product Collection and Venous Blood Sample ^u	X ^g	X	X	X	X	X	X	X	X ^h	
Treatment Compliance		X	X	X	X	X	X	X	X ^h	
Take Study Drug Dose in Clinic ^v	X ^w							X	X ^h	
Daily Self-Administration of Study Treatment ^v		X								
MIQ ^x	X ^g	X	X	X	X	X	X	X	X ^h	X
UFS-QoL Questionnaire ^x	X ^g			X				X	X ^h	
EQ-5D-5L Questionnaire ^x	X ^g							X	X ^h	
Adverse Event Collection ^y	X ^z	X	X	X	X	X	X	X	X	X
Status of Menstruation Recovery										X ^{aa}

BP, blood pressure; ECG, electrocardiogram; EQ-5D-5L, European Quality of Life Five-Dimension Five-Level Scale; HR, heart rate; MIQ, Menorrhagia Impact Questionnaire; UFS-QoL, Uterine Fibroid Symptom and Health-Related Quality of Life

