- ^s Endometrial biopsies are to be performed per instructions in the parent study. See the Laboratory Manual for guidance on handling and shipping the biopsy sample to the central laboratory for analysis. An endometrial biopsy will have been performed at the parent study Week 24 visit for all patients who participated in MVT-601-3001 (see MVT-601-3001 protocol for details) and in some patients who participated in MVT-601-3002 (see MVT-601-3002 protocol for details).
- ^t Patients enter diary information on menstruation status and feminine product use daily starting on the day of the Week 24/Baseline Visit.
- ^u A venous blood sample (for hemoglobin) must be collected each time feminine products are collected to be sent to the central laboratory conducting the alkaline hematin assessment. The site must document the start and stop dates of the patient's menses corresponding to the collected feminine products.
- ^v Patients will take the first dose of the study drug for this study once daily starting with the Week 24/Baseline visit (taken at the visit). The first dose of study drug for this extension study must not be taken until all parent study Week 24 procedures such as laboratory tests have been completed. The last dose of study drug will be taken in the clinic during the Week 52/Early Termination visit.
- ^w Pregnancy test must be negative before the study drug dose is administered.
- ^x The patient will enter her response(s) into an electronic tablet device at the site.
- ^y Collect adverse events from the time that the first dose of study drug for MVT-601-3003 is administered. Adverse events with onset prior to the first dose of study drug for MVT-601-3003 should be reported as an adverse event in the parent study (MVT-601-3001 or MVT-601-3002). If events originating in the parent study are ongoing at the time of the first dose of study drug for MVT-601-3003, please see the Study Reference Manual for instructions for recording the follow-up status.
- ^z Adverse events are collected for both the parent study and for MVT-601-3003 at the Week 24/Baseline visit (see footnote v for further details).
- ^{aa} Patients whose menses have not resumed as of the Follow-up visit for whom there is no explanation for the lack of resumption (eg, medical procedure or medications) will be contacted again by telephone 3 (+0.5) months after the Follow-Up visit to determine if menses has resumed and questioned about factors that may affect resumption of menses.

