4.5. Removal of Patients from Therapy

Completion of the Week 52 visit defines completion of the study. Patients may withdraw consent to participate in the study and discontinue treatment at any time for any reason. Investigators or the medical monitor may remove patients from therapy under this protocol for reasons of safety and/or lack of compliance as discussed below. Patients removed from therapy for any reason will undergo the assessments for the Early Termination visit (see the Week 52 visit on the Schedule of Activities, Section 1.1) and will have a Follow-up visit to assess safety approximately 30 days after the end of study drug treatment (ie, after the patient's last dose of study medication).

The following safety and/or compliance events will result in the removal of patients from therapy either permanently or until the etiology of the problem has been identified and resolved:

- Any adverse event that is intolerable to the patient and that cannot be ameliorated by the use of adequate medical intervention, or that in the opinion of the investigator or medical monitor would lead to undue risk to the patient if dosing continued;
- If it is discovered after enrollment that a patient failed to meet protocol entry criteria and continued participation poses an unacceptable risk to the patient's health;
- If the following liver test abnormalities develop, study drug should be discontinued immediately with appropriate clinical follow-up (including repeat laboratory tests, until a patient's laboratory profile has returned to normal/baseline status):
 - ALT or AST > 8 x ULN; or
 - ALT or AST > 5 x ULN and persists for more than 2 weeks; or
 - ALT or AST > 3 x ULN in conjunction with elevated total bilirubin > 2 x ULN or international normalized ratio (INR) > 1.5; or
 - ALT or AST > 3 x ULN with appearance of fatigue, nausea, vomiting, right upper quadrant pain or tenderness, fever, rash and/or eosinophilia (> 5%);
- QT interval by the Fridericia correction (QTcF) prolongation of more than 500 msec read by a cardiologist;

-
- Evidence of endometrial hyperplasia or endometrial carcinoma on endometrial biopsy;
 - If the patient has a $\geq 7\%$ loss of bone mineral density at lumbar spine, total hip, or femoral neck compared with the parent study Baseline;

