 - If the patient, in the opinion of the investigator or the medical monitor, is grossly noncompliant with the protocol's requirements. This may include $< 75\%$ compliance with the study drug for at least 2 months; not returning any feminine products despite having menstrual bleeding for > 2 consecutive cycles; or missing multiple study visits;
 - If the patient becomes pregnant at any time after providing a signed informed consent form, the patient must be withdrawn immediately (see Section 7.8 for information on pregnancy reporting).

Should a patient fail to attend the clinic for a required study visit within the protocol-defined window, the site should attempt to contact the patient and reschedule the missed visit as soon as possible. The site should also counsel the patient on the importance of maintaining the assigned visit schedule and determine whether the patient can and/or should continue in the study based on previous noncompliance. In cases where the patient does not return for the rescheduled visit or cannot be reached to reschedule the missed visit, the site should make every effort to regain contact with the patient. The site should attempt at least three documented telephone calls and if necessary a certified letter to the patient's last known mailing address so that they can appropriately be withdrawn from the study with a primary reason of "Lost to Follow-up."

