6.3. Early Termination Visit and Follow-up Visit

All patients withdrawing from the study prior to Week 52 will complete an Early Termination visit. The Early Termination visit procedures are identical to those of Week 52; however, for patients whose last dose of study drug is during Week 32 or earlier, the following procedures do not need to be performed: transvaginal ultrasound (with or without a transabdominal ultrasound), bone densitometry, and endometrial biopsy. These procedures may be performed at the investigator's discretion if they aid in follow-up of ongoing adverse events.

Patients (including those who complete the Week 52 visit and those who withdraw early from this study) will have a Follow-up visit approximately 30 days after the last dose of study drug, or prior to the date of initiation of another investigational agent or hormonal therapy affecting the hypothalamic-pituitary-gonadal axis or surgical intervention or other invasive procedure for uterine fibroids, whichever occurs first. However, for patients who enroll directly into another relugolix clinical study upon completion of the Week 52 visit, then the Follow-up visit may be waived.

The Follow-up visit will be used to assess safety after discontinuation of study treatment including adverse events, clinical safety laboratories, and return of menstruation. Refer to the Schedule of Activities (see Section 1.1) for individual study visit procedures during the Follow-up visit.

At an Early Termination visit occurring on or after Week 36, patients with a bone mineral density loss of > 3 relative to the parent study Baseline measurement will undergo a follow-up bone densitometry scan at 6 (± 1) months and will be contacted to question them about medications and conditions (eg, pregnancy) that might affect bone mineral density through the time of follow-up bone densitometry. If Early Termination occurs prior to Week 36, follow-up bone densitometry will be performed according to the requirements of the parent study. The follow-up bone densitometry will be submitted for central reading.

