7.8. Pregnancy Reporting

If any patient becomes pregnant during the study, the site must discontinue the patient from the study treatment immediately and have her return for an Early Termination visit.

If the patient agrees, the investigator should notify the patient's primary care physician of the pregnancy and provide details of the patient's participation in the study and treatment.

A pregnancy is to be reported to the sponsor within 24 hours of awareness by the study site personnel, using the pregnancy report forms and contact information in Section 7.6. The expected date of delivery or expected date of the end of the pregnancy, last menstruation, estimated conception date, pregnancy result, and neonatal data, etc, should be included in this information, as available.

The investigator will follow the medical status of the mother, as well as the fetus, and will report the outcome to the sponsor.

7.9. Vital Signs, Physical Examinations, Clinical Laboratory Tests, Electrocardiograms, and Bone Mineral Density Measures

Section 6.6.2 details the requirements for measurement of safety parameters including vital signs, weight, physical examinations, clinical laboratory tests, ECGs, and bone mineral density.

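### The clinic dose at Early Termination has no exception for a woman whose study drug was already permanently stopped for pregnancy or a liver criterion

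*Protocol*

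**What the plan says.** In Table 1 of the protocol (Section 1.1), the row "Take Study Drug Dose in Clinic" has an X in the column that serves both Week 52 and Early Termination of study drug. The X carries no qualifying footnote of its own. Footnote v, attached to the row, adds: "The last dose of study drug will be taken in the clinic during the Week 52/Early Termination visit". Footnote n, on pharmacodynamic sampling, tells sites to give study treatment once the samples are drawn, and Week 52/Early Termination is a sampling visit.

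Section 6.3 says "The Early Termination visit procedures are identical to those of Week 52". Where a woman took her final dose no later than Week 32, the section adds a relaxation: "the following procedures do not need to be performed: transvaginal ultrasound (with or without a transabdominal ultrasound), bone densitometry, and endometrial biopsy". The clinic dose is not among these waivers.

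On stopping, Section 4.5 says of the liver criteria that "study drug should be discontinued immediately with appropriate clinical follow-up", and of pregnancy, "If the patient becomes pregnant at any time after providing a signed informed consent form, the patient must be withdrawn immediately". Section 7.8 gives the order of events in pregnancy: "the site must discontinue the patient from the study treatment immediately and have her return for an Early Termination visit". For removals generally, Section 4.5 states: "Patients removed from therapy for any reason will undergo the assessments for the Early Termination visit (see the Week 52 visit", and refers on to the Schedule.

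**The concern.** Some women reach the Early Termination visit because their drug has already been stopped. For them the last dose lies in the past, yet the Schedule places it at that visit and states no exception. Taken at its word, the Schedule would have a site give one more dose of relugolix with estradiol and norethindrone acetate to a woman known to be pregnant, or to one permanently stopped for a liver signal.

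Sites are told to work from the Schedule (Section 6.1) and not to deviate from the protocol without approval, medical emergencies apart (Section 10.2.1). A site that rightly withholds the dose therefore departs from footnote v. A stated dosing rule should not be wrong for exactly the women whom the stopping rules protect.

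**Working it through.** The plan gives no figure on this point, so the check is a comparison of texts.

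1. **Where a dose at Early Termination comes from.** Two places put it there directly: the Table 1 cell and footnote v. Two more carry it over: Section 6.3, by making the visits' procedures the same, and footnote n, by telling sites to dose after sampling. Section 6.3 waives 3 procedures (ultrasound, bone densitometry, biopsy). The number of these that are the clinic dose is 0.

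2. **Pregnancy.** Section 7.8 stops treatment first and has the woman return afterwards. Her last dose is therefore no later than the stop, and the stop precedes the visit: last dose ≤ stop < Early Termination. Footnote v requires last dose = Early Termination. Both cannot hold.

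3. **Liver criteria.** Section 4.5 lists 4 triggers, each calling for immediate discontinuation. Its lead sentence allows removal to be permanent or to last until the cause is found and resolved, so there are two cases. A woman stopped permanently goes to Early Termination with her last dose behind her, and the conflict is the same as in step 2. A woman withheld temporarily under Section 7.5.1 who then resumes has no Early Termination visit on that account, so there is no conflict for her.

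4. **Search for an exception.**
   - Section 5.4 names Week 24/Baseline and Week 52 as clinic dosing days. It neither mentions nor excludes Early Termination, and it points back to the Schedule.
   - Footnote p recognises that the last dose can precede the visit, but it is attached only to ultrasound, densitometry and biopsy.
   - Footnote w requires a negative pregnancy test before dosing. In the dosing row it is attached only to the Week 24/Baseline cell. The Week 52/Early Termination column contains both a urine pregnancy test and a dose, with no stated order between them.
   - Section 5.5 (written sponsor approval to restart) and Section 7.5.1 (limits on rechallenge) restrict resumption in general. Neither amends the Schedule.

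5. **Size.** Excess = 1 visit × 1 daily dose = at most one dose per affected woman (relugolix 40 mg, estradiol 1.0 mg, norethindrone acetate 0.5 mg). The documents give no expected number of affected women.

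6. **Analysis.** SAP Sections 4.3.2 and 4.3.5 take the last-dose date as the date a dose was actually received and compute duration as last date − first date + 1. The final feminine product window in SAP Table 7 is also keyed to that date. None of these assumes that the dose falls at Early Termination. A woman's values would shift only if a wrong dose were really given.

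**The case against.** The strongest reply is that the dosing row governs place and timing for a woman still on drug. Section 5.4 describes taking the dose in the clinic instead of at home, and Section 6.6.1.4 explains why: estradiol is sampled before dosing. On that reading nobody is told to restart a stopped drug. The specific safety rules in Sections 4.5, 5.5, 7.5.1 and 7.8 would also ordinarily prevail over a general schedule cell, and Table 6 repeats immediate withdrawal for pregnancy. Section 4.5 sends removed patients for assessments, and taking a tablet is not an assessment. No post-baseline home dose depends on a pregnancy test, so gating one more dose adds little. Section 6 also leaves procedural detail to the Study Reference Manual, which is not available here.

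Much of this stands. The intended meaning is very probably the sensible one, and a careful site would follow the stopping rules. Section 4.5 by itself does not carry the dose over; Section 6.3 does that. Women who are withheld and then resume do not belong in the affected group.

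The wording remains wrong all the same. For pregnancy, Section 7.8 and footnote v prescribe incompatible times for the last dose, and the text does not say which governs. On the test, the sample is already scheduled at the same visit as the dose, so putting it first costs nothing.

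A reader might infer that the protocol intends to dose pregnant women or women with liver injury, or that such dosing is to be expected. The documents do not support that: every section that deals with these women tells the site to stop.

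**Conclusion.** This is a minor drafting conflict with a safety implication. The clinic-dose cell and footnote v, supported by Section 6.3 and footnote n, place the last dose at Week 52/Early Termination. They make no exception for a woman already permanently stopped, contrary to Section 7.8 for pregnancy and Section 4.5 for the liver criteria.

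Actual mis-dosing is unlikely, the ceiling is one dose per affected woman, and the analysis is unaffected. The conclusion assumes that the Study Reference Manual is not relied on to correct the protocol's own wording. It does not extend to women who resume after a temporary hold, and it is no evidence of a flaw in the stopping rules, which are explicit. It is worth correcting because the rule as written is wrong for a small group at particular risk and the correction is nearly free.

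**What to change.** Qualify footnote v, footnote n and Section 6.3 so that the clinic dose is taken at Week 52, or at Early Termination only by a woman who is still on study drug and meets no stopping or withholding criterion. Footnote n has to be included, because otherwise it would still tell sites to dose after sampling at that visit.

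Attach footnote w to the Week 52/Early Termination cell of the dosing row, so that the pregnancy test already scheduled there is read before the dose.

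The cost is three short phrases and one footnote marker. No procedure is added and the SAP does not change.

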2. INTRODUCTION

2.1. Uterine Fibroids with Heavy Menstrual Bleeding

Uterine leiomyomas (often referred to as fibroids or myomas) are common benign, estrogen-dependent tumors that grow in the muscular wall of the uterus and occur in approximately 25% of women of reproductive age. While the majority of uterine fibroids are asymptomatic, approximately 25% of women with fibroids develop symptoms requiring treatment. The most problematic symptom for women with uterine fibroids is heavy menstrual bleeding, with menstrual periods of increased duration and volume. In women with uterine fibroids, menstrual periods can last as long as 10 to 14 days rather than the usual 5 to 7 days, and blood loss can be as high as 300 to 500 mL, with anything more than 80 mL during a given cycle considered abnormal. The heavy menstrual bleeding associated with uterine fibroids is likely caused by the increase in surface area of the uterine cavity, poor uterine contraction due to the myoma, and increased circulation, congestion, or impaired hemostasis due to hypertrophy of the endometrium near the myoma [Hapangama, 2016]. Persistent heavy menstrual bleeding can induce iron-deficiency anemia and associated fatigue and loss of energy. Heavy menstrual bleeding is a primary reason for the deterioration in the health-related quality of life assessed in patients with uterine fibroids and is a major cause of elective hysterectomy. Other symptoms include bulk symptoms, such as pain or pressure in the abdomen and pelvis due to large myoma(s), low back pain, urinary frequency or urinary tract obstruction, constipation, and pregnancy loss.

The incidence of uterine fibroids increases as women grow older, and risk factors include nulliparity, obesity, family history, black race, and hypertension. Fibroids typically arise during the reproductive years, tend to enlarge during pregnancy, and regress after menopause as these tumors are dependent upon estrogen and progesterone for their growth. Transvaginal ultrasound is used most commonly to diagnose these benign tumors, and magnetic resonance imaging, sonohysterography, and hysteroscopy are used to evaluate their size and position. The type of treatment recommended for uterine fibroids typically depends upon their size, location, the patient's age, reproductive plans, and obstetrical history. Few medical options are available for women with heavy menstrual bleeding associated with uterine fibroids and approximately 60% of women who received medical therapy in one study underwent a surgical procedure within 2 years [Marjoribanks, 2006], suggesting many women are inadequately treated with the currently available medical therapies.

Gonadotropin-releasing hormone (GnRH) agonists such as leuprolide acetate (also known as leuprorelin) are effective in lowering estrogen and progesterone levels, decreasing menstrual bleeding, and decreasing fibroid size, however they cannot be used for more than 6 months due to bone mineral density loss from the resulting hypoestrogenic state. The GnRH agonists, which are administered by injection at 1- or 3-month intervals, first stimulate secretion of luteinizing hormone (LH) and follicle-stimulating hormone (FSH), which, in turn, increase estradiol and progesterone levels resulting in a flare of clinical symptoms. This initial rise in hormonal levels is followed by a gradual decline in levels over 4 weeks as the pituitary becomes desensitized to the chronic stimulation of the GnRH agonist and LH and FSH levels fall. Other medical treatments are used but have limited clinical effectiveness, including tranexamic acid, aromatase inhibitors, nonsteroidal anti-inflammatory medications, and danazol.

The current mainstay of treatment for women with heavy menstrual bleeding associated with uterine fibroids is surgery. Several surgical procedures are frequently performed including myomectomy by various techniques, endometrial ablation, endometrial uterine artery embolization, and magnetic resonance-guided focused-ultrasound surgery. Each of these procedures has complications. For example, abdominal myomectomy results in complications requiring hysterectomy in up to 3 to 4% of cases, along with the frequent development of intraoperative adhesions [Gliklich, 2011]. Furthermore, recurrence after myomectomy is common, with at least 25% of women requiring additional treatment [Stewart, 2015; Marret, 2012; ACOG Practice Bulletin No. 96, 2008]. Hysterectomy is the definitive procedure, and more than 200,000 hysterectomies are performed annually in the United States (US) for uterine fibroids [Farquhar, 2002; Wu, 2007]. Major complications have been reported to occur in up to 25% of women undergoing hysterectomy, including infection, severe bleeding, and injuries to the urethra, bowel, or bladder. One study showed that among women with Medicaid insurance who underwent abdominal hysterectomy, there was a 10% risk of transfusion and up to a 28% risk of medical or surgical complications including major blood loss, wound infection, and febrile episodes [Gliklich, 2011].

Approximately 3 million women in the US suffer from symptomatic uterine fibroids that are inadequately treated with medical therapy, and related US health care costs for uterine fibroids exceeds \$34 billion [Stewart, 2015; Cardozo, 2012; Gliklich, 2011]. There is a great need for a medicine that can decrease the symptoms of uterine fibroids and can be safely administered so that women have an option other than surgical procedures such as myomectomy and hysterectomy.

